4.3 Exclusion Criteria

Subjects presenting with any of the following will not be included in the study:

- Poor prognosis as judged by Apache II score >25
- Pregnant females
- Grossly under- or overweight (BMI <18 or >29)
- Ongoing therapy with a macrolide (clarithromycin, erythromycin, azithromycin, telithromycin)
- Known allergy to any macrolides
- Proven *P. aeruginosa* pneumonia (with documented CFU>10⁴ in BAL or PBS)
- Ongoing antipseudomonal therapy with a susceptible colonizing strain as proven by antibiogramme*

* A list of recommended antibiotics deprived of antipseudomonal activity is provided in Section 6.2 to facilitate the choice of the investigators and to homogenize antibiotic treatment according to type of infections. For patients on antibiotherapy with activity against pseudomonas prior to study entry, they will be maintained in the screening phase for 48 hrs, pending results of antibiogramme on the colonized strain. If found to be susceptible to the antibiotic used, the patient will be excluded from the study; if found to be resistant, the patient will be included in the study (also see Section 6.2)

- Anticipated short duration of mechanical ventilation (≤ 3 days)
- Known drug interaction which could interfere enough with absorption, metabolism, or excretion and thus could decrease efficacy or raise safety concern despite plasma drug monitoring of concomitant therapy (for examples see Section 6.2)
- Severe hepatic insufficiency (type C i.e. score >10 on Child Pugh scale, Appendix A) [Pugh et al 1973]
- Sick sinus syndrome or known long QT syndrome or $QTc >500$ msec
- Recent donation of blood or participation in another clinical trial within 3 months (Europe) or 1 month (USA)
- Any situation exposing the patient to higher risk or possibly confounding results of the study

Any local or country specific regulations must be respected. Any waiver of the inclusion and exclusion criteria listed above must be approved by the investigator and by the monitor on a case-by-case basis prior to enrolling the subject. This must be documented by both the monitor and the investigator.

No subject will be allowed to enroll in this study more than once if study drug was administered. However a patient may be screened on a 2nd occasion under another screening number if he did not meet all inclusion and exclusion criteria in the first instance.

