11.2 Study Populations

- All subjects who are considered as available and interpretable will be included in the clinical and pharmacodynamic analysis, providing they have completed at least 3 days of treatment prior to exitus or at least 5 days prior to extubation, and providing no major protocol violations have been identified. Cases with death occurring within 3 days of entering study and apparently triggered by other causes than *P.aeruginosa* pneumonia will not be considered as assessable
- All randomized subjects who will have received at least one dose of medication and having data considered as available and interpretable will be included in the safety analysis.

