12.5 Protocol Amendments

Neither the investigator nor the sponsor's representatives will alter this study protocol without obtaining the written agreement of the other. Once the study has started, amendments should be made only in exceptional cases. The changes then become part of the study protocol.

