12.6 Approval of the Study Protocol and Amendments

Before the start of the study, the study protocol, informed consent document, and any other appropriate documents will be submitted to the Ethical Review Committee (ERC) with a cover letter or a form listing the documents submitted, their dates of issue, and the site for which approval is sought. Before the study initiation, the sponsor will notify the authorities according to local legal requirements.

Study medication can only be supplied to the investigator after documentation on **all** ethical and legal requirements for starting the study has been received by the sponsor. This documentation must also include a list of the members of the ERC, including their gender, occupation, and qualifications. The opinion given by the ERC should specify the study title, study code, study site, amendment number if appropriate and any other documents reviewed. It must mention the date on which the decision was made and must be officially signed by a committee member, usually the president or secretary to the ERC. In the USA an FDA Form 1572 must be filled.

Before the first subject is enrolled in the study, all ethical and legal requirements must be met.

The ERC and, if applicable, the authorities must be informed of all subsequent protocol amendments, in accordance with the national legal requirements. Amendments must be evaluated to determine whether formal approval must be sought and whether the informed consent document should also be revised.

The investigator must keep a record of all communication with the ERC. This also applies to any communication between the investigator and the authorities.

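### Section 4.3 lets the investigator and the monitor waive any listed entry criterion for a single patient, including the safety exclusions and the exclusion of existing P. aeruginosa pneumonia

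*Protocol*

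**What the plan says.** Protocol Section 4.3 opens by ruling out anyone who presents with any item on its list. The items include safety exclusions such as macrolide allergy, pregnancy, severe hepatic insufficiency and "Sick sinus syndrome or known long QT syndrome" or a QTc above 500 msec. They also include items that define the trial's question: ongoing therapy active against the colonising strain, and proven *P. aeruginosa* "pneumonia (with documented CFU>10⁴ in BAL or PBS".

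Below the list the section adds: "Any waiver of the inclusion and exclusion criteria listed above must be approved by the investigator and by the monitor on a case-by-case basis". Approval must come before the patient is enrolled. On records it says: "This must be documented by both the monitor and the investigator". The only limit placed beside the clause is "Any local or country specific regulations must be respected". The following paragraph allows a patient who failed the criteria to be screened a second time under a new screening number.

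Other sections bear on the point:

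- Section 4.1 stops recruitment once 10 cases of *P. aeruginosa* pneumonia have been confirmed by the blinded panel. Section 7.2.4 sets a ceiling of 240 patients entered.
- Sections 7.2.4 and 11.4 give the panel the task of confirming the diagnosis.
- Section 11.2 admits patients to the efficacy analysis "providing no major protocol violations have been identified".
- Section 11.3 tests occurrence of pneumonia by Fisher's exact test, two-sided at 0.10.

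**The concern.** The same section first excludes certain patients and then lets two people on the trial admit them one at a time. Of the two, one is the physician who wishes to enrol the patient. The other is a monitor, whose work in Section 13.1 is to review case report forms and source documents and to check that the protocol is followed. No second physician is required.

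Two things are at stake. The first is safety: a patient can receive study drug despite an exclusion written for that patient's protection. The second is the population. This is a prevention trial, and the exclusion of existing pneumonia keeps out patients who already have the outcome. The requirement of colonisation and the exclusion of active antipseudomonal therapy define who is at risk of it. All of these can be waived. With about 10 events in the whole trial, each case that does not belong to the question is a visible share of the evidence.

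**Working it through.** **1. How many events the trial rests on.** Inputs: 10 cases, 10% occurrence on placebo (Sections 4.1 and 11.5), equal groups (Section 5.3). Assessable patients needed = 10 / mean event rate.

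- No effect: 10 / ((0.10 + 0.10)/2) = 100.
- Complete protection: 10 / ((0.10 + 0)/2) = 200.
- Adding 20%: 100 × 1.2 = 120 and 200 × 1.2 = 240.

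These match the protocol's 100 to 200 assessable and 120 to 240 recruited. Whatever the total, the comparison rests on about 10 events.

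**2. What the waiver reaches.** It applies to the inclusion and exclusion criteria as listed, without exception. Consent is outside its practical reach, because Sections 4.2 and 12.3 require it separately for every subject.

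**3. Whether a waived prevalent case could count.** The exclusion uses a count above 10⁴ in BAL or PBS. The case definition in Section 7.2.4 uses at least 10⁴ in BAL or at least 10³ in PBS, with a CPIS of at least 6. Any count that meets the exclusion therefore already meets the culture part of the case definition. If the CPIS is also 6 or more, the patient fits the definition on entry. The panel receives CPIS values, X-rays and culture results, but neither Section 7.2.4 nor Section 11.4 tells it to set aside pneumonia present at entry.

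**4. Size.** One such patient is 1/10 = 10% of the stopping events, and two are 2/10 = 20%. The share per patient would be larger if the ceiling of 240 were reached before 10 cases.

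**5. Direction.** Section 4.3 places approval before enrolment, and Section 5.3 assigns the randomisation number from Day 1. If those approving a waiver do not know the next allocation, a prevalent case falls in either arm with probability 1/2. Take the protocol's complete-protection scenario and let one of the 10 cases be prevalent:

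- placebo: 9 + 0.5 = 9.5 expected;
- azithromycin: 0 + 0.5 = 0.5 expected, instead of 10 and 0.

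In the no-effect scenario the expected split stays 5 to 5. The expected movement is towards no difference.

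**6. What cannot be computed.** The protocol gives no frequency of waivers and no indication of which criteria would be waived, so an expected effect on the p-value cannot be derived.

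**The case against.** The best defence is that the clause is a control: prior approval, two parties, case by case, documented, and subject to local rules. The monitor acts for the sponsor under Section 13.1, so the sponsor is arguably represented. That stands as traceability. It does not supply a medical review beyond the enrolling investigator, and it protects no criterion. Naming a sponsor physician would help on safety but would still let patients outside the target population in.

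Some cases are also partly caught elsewhere. Section 6.2 repeats that a patient on an antibiotic to which the strain is susceptible is excluded, forbids other macrolides during the study, and takes a patient out once pneumonia is diagnosed. Section 11.3 analyses patients on active antibiotics as a subgroup. CPIS is recorded on Day -1 and Day 1, so the panel could see early disease. These points reduce the risk but do not remove it. Leaving the study at diagnosis is also how a case is reached, so it does not stop a prevalent case from counting.

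Three stronger readings are tempting and are not supported:

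- *The waiver breaches Sections 12.5 and 12.6.* Those sections concern changes to the protocol: "Once the study has started, amendments should be made only in exceptional cases" and "The ERC and, if applicable, the authorities must be informed of all subsequent protocol amendments". The waiver rule is itself part of the protocol submitted to the ethics committee, so using it is not an unreported amendment.
- *Waived patients can be kept or dropped once outcomes are known.* Section 11.2 does not define a major violation, but that can be left to the statistical plan, which Section 11.3 requires before decoding.
- *A waiver can flip the result.* With 75 per arm, Fisher's two-sided p is 0.098 for 8 versus 2 cases and 0.327 for 7 versus 3. That contrast needs a case to change arm, which a waiver cannot cause. Dropping one case works in either direction: 7 versus 2 gives 0.166 and 8 versus 1 gives 0.034. At 100 per arm, 8 versus 2 already misses the level (0.1005). These figures show how fragile 10 events are, not the effect of a waiver.

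**Conclusion.** The point holds as a defect of Section 4.3. The waiver clause contradicts the section's own exclusion rule, covers every listed criterion, and asks for no physician's agreement beyond the enrolling investigator's. As written, it allows patients with safety exclusions to be dosed and patients outside the target population to be randomised.

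The size that can be stated is 10% of the stopping events for each waived prevalent case that the panel confirms. This assumes that such a waiver is granted, that the CPIS requirement is met, and that 10 cases are reached. The likely statistical consequence is dilution, given that allocation stays concealed when the waiver is approved. The documents do not support a claim of bias towards one arm or of a particular change in the p-value. The change is worth making because it protects patients and the population at almost no cost.

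**What to change.** Delete the two waiver sentences in Section 4.3 and state that no waivers of entry criteria are granted. A patient who fails a criterion is recorded as a screen failure and may be screened again, as the next paragraph of Section 4.3 already permits. If a criterion proves unworkable, change it for all sites by amendment through Sections 12.5 and 12.6. None of this alters a clinical threshold.

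The cost is two deleted sentences, one added, and a few more screen failures, partly recovered by re-screening.

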5. STUDY TREATMENTS

5.1 Details of Study Treatments

Treatment

Drug code	ANB 006
INN	Azithromycin (dihydrate) MW 785.0
Dosage form	Glass vials, 10 mL, sterilized Lyophilized azithromycin 500 mg Inactive ingredients (413.6 mg citric acid and sodium hydroxide) Under vacuum
Route	i.v. solution in sterile 0.9% sodium chloride, 250 mL, in sterile pouch Administered as 1 hour infusion (1.2 mg/mL) after reconstitution in 2 steps For details, see Appendix C
Dose	300 mg
Duration	Multiple dose, once a day, for a maximum of 20 days
Manufacturer	Ben Venue Laboratories Inc. Single commercial batch USA The batch number and the expiration date of lyophilized material will be recorded in the Clinical Study Report.
Clinical supplies	No specific release required since commercial batch used without re-packing Study label printed and affixed by Quintiles on each vial

Placebo

Dosage form	Not applicable
Dose	0 mg
Route	i.v. solution of sterile 0.9% sodium chloride, 250 mL, in sterile pouch Administered as 1 hour infusion after reconstitution in 2 steps For details, see Appendix C
Manufacturer	To be purchased locally by each local hospital pharmacy as a single batch The source, batch number and the expiration date of lyophilized material will be recorded in the Clinical Study Report.

Subjects will be administered i.v. from infusion pouches as a solution of 250 mL containing 300 mg azithromycin in saline at 1.2 mg/mL or normal saline (placebo), over 1 hour.

Vials with lyophilized material can be stored at room temperature (30 °C or 86 °F and below). After reconstitution, azithromycin solutions (100 mg/mL and 2 mg/mL) can be stored for 24 hours at or below room temperature (30 °C or 86 °F) or for 7 days if stored under refrigeration (5°C or 41°F).

5.2 Dosage Schedule

At each study site, the study medication will be prepared by the hospital pharmacist, using the method described in Appendix C, the randomization numbers allocated to the site and the randomization code provided by the independent statistician. The pouches will be infused i.v. by the investigator or his delegate, carefully following the procedures set out in this study protocol. Administration of study drug will be time zero, Day 1 (i.e. t=0 start of infusion) and the i.v. infusion will last 1 hour. Exact date, start

and completion time of infusion will be recorded daily in the case report form (CRF). If a central line is available, the study drug will be preferably infused by that port, avoiding any other concomitant infusion.

Efforts will be made to comply with a 24 hour interval between daily doses for a given patient throughout the treatment period as much as technically feasible. The maximum duration of treatment will be 20 days.

5.3 Treatment Assignment

The study medication will be administered only to subjects included in this study following the procedures set out in the study protocol.

Since the screening period is expected to be short, no dedicated **subject numbers** will be allocated in advance but only a simplified code combining centre number (1, 2, 3, ...), letter S (for screening), and the chronological number of entry (1,2,3,...). Thus, in Centre 5, the 11th patient screened would have the subject number **5-S11**, and, in Centre 12, the 2nd patient screened would carry the subject number **12-S2**. This subject number will be used to identify the subject between initiation and completion of screening, with verification of inclusion/exclusion criteria, and on Day -1. Thereafter, starting on Day 1, each subject will be assigned a **randomization number**, both sequentially and in chronological order, which will combine the study site number and a study medication number i.e. #05108 for centre 5 and 8th patient. Each patient will receive the corresponding study medication (placebo or azithromycin), labeled with that same code number. The investigator will record in the CRF the subject screening number and the 5-digit randomization number.

The study medication will be randomly assigned in advance to the randomization numbers taken into consideration the study site (#01101 to 01124 for centre 1) for a maximum of 25 study sites although 20 sites are targeted initially, according to the randomization plan generated by the Biometrics Department of Quintiles for each site and following a balanced basis (equal groups), by blocks of 4. Each centre will have a different allocation schedule. Each centre will initially receive the number of azithromycin vials corresponding to treatment for 25% of committed patients assuming 20 days of treatment (2 boxes of 10 vials per patient) and taking into account the anticipated patient recruitment (8, 12, 16, 20,...) Additional vials will be shipped to each centre based on recruitment and duration of treatment. Supplementary azithromycin vials will be maintained at disposal of centers recruiting beyond original plans or for new centres in case of need. The randomization plans will be stored with the Biometrics Department. Subjects withdrawn from the study will retain their subject number and their randomization number if drug has already been administered. New subjects must always be allotted a new subject number.

Study medication will be prepared by the hospital pharmacist in accordance with the randomization lists prepared by an independent statistician. All randomization schedules will be stored with the hospital pharmacist. The investigator and the ICU will receive sealed individual envelopes (see below Section 5.4).

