PROOF-OF CONCEPT STUDY TO INVESTIGATE THE IMPACT OF AZITHROMYCIN ADMINISTERED I.V. VS. PLACEBO ON THE PREVENTION OF PNEUMONIA IN VENTILATED PATIENTS COLONIZED WITH *PSEUDOMONAS AERUGINOSA*

Coordinating Investigator

[name], Paris

Centre xx

Principal Investigator

Department

Hospital

Address

City, mail code

Country

List of Centres by Country

Each country centre list will include:

- National Coordinating Investigator
- Each site with:
 - Site number
 - Principal Investigator
 - Subinvestigators
 - Address
- Quintiles Study Monitor(s)

Phase IIa

Multinational and multicentric

Indication

Prevention of pneumonia in ventilated patients colonized with *Pseudomonas aeruginosa*

Objectives

Primary objective

- To assess the clinical efficacy of azithromycin 300 mg i.v., used as a quorum-sensing blocker, compared to placebo for preventing or delaying the occurrence of pneumonia in ventilated patients colonized with *Pseudomonas aeruginosa*

Secondary objectives

- To assess other clinical efficacy variables
- To compare safety profile in target population
- To demonstrate using both *in vivo* and *in vitro* parameters whether azithromycin can be used clinically as a quorum-sensing blocker against *P. aeruginosa*
- To determine whether *P. aeruginosa* can develop resistance to the quorum-sensing blocker effect of azithromycin

- To check whether prolonged treatment with azithromycin may induce resistance to any of 11 antipseudomonal antibiotics (list in Section 6.2.)
- To verify whether emergence of resistance to other bacteriae may be elicited by assessing rate of infections in both study groups (azithromycin vs. placebo)

Design

2-parallel groups, double blind, randomized, placebo controlled, multiple i.v. dose administered once daily

Population

- Intubated patients
- Age 18 to 75 years
- Males and non pregnant females
- Respiratory tract colonized by *Pseudomonas aeruginosa* as documented by tracheal aspirate

Sample size

- Recruit a total of 120 to 240 patients in order to achieve 100 to 200 assessable cases
- Stop recruitment when 10 *P. aeruginosa* pneumonia cases have been documented and confirmed by panel of experts under blinded conditions

Treatments

- 300 mg azithromycin as i.v. solution at 2 mg/mL or saline (placebo), infused daily over 1 hour, until extubation (Day n-1), occurrence of pneumonia (Day x), exitus, or for a maximum of 20 consecutive days (Day 20)

Clinical efficacy (clinical site)

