5.5 Supplies and Accountability

The site pharmacist will inventory and acknowledge receipt of all shipments of study medication which must be kept at room temperature or below, pending preparation and dilution as stated above under Section 5.4. and in Appendix C.

All study medication must be kept in a locked area with access restricted to designated study personnel. The investigator and pharmacist will also keep accurate records of the quantities of study medication prepared and dispensed. During the study the monitor will inquire at regular intervals (such as every 4 patient block) on number of available azithromycin vials. The site monitor will check the supplies of study medication held and dispensed by the pharmacist and administered by the investigator to ensure accountability of all study medication used, but only after study completion, after the database has been frozen, and the code has been unblinded. At the conclusion of the study, all unused study medication and all medication containers will be destroyed locally under appropriate control and documentation unless other arrangements have been approved with the sponsor's representatives. A final report of drug accountability as agreed with the site monitor will be prepared and maintained by the pharmacist.

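### The protocol prints a single fixed block length of 4 per centre, so a patient unmasked in positions 1 to 3 of a block makes later allocations in that block partly predictable

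*Protocol*

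**What the plan says.** Protocol Section 5.3 has the plan generated "for each site and following a balanced basis (equal groups), by blocks of 4" and adds: "Each centre will have a different allocation schedule". Patients receive a number "both sequentially and in chronological order, which will combine the study site number and a study medication number". The number range for a site is illustrated by "01101 to 01124 for centre 1". The same section lists anticipated recruitment per centre in multiples of four.

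Section 5.5 has the monitor ask about the azithromycin vials in stock at intervals "such as every 4 patient block".

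On code breaking, Section 5.3 states: "The investigator and the ICU will receive sealed individual envelopes". Section 10.2 lets the investigator or an authorized person open an envelope when knowledge of the treatment is medically imperative.

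Section 14.2 shows that the investigator signs the protocol. No varying or withheld block length is mentioned.

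**The concern.** Blocking within centre protects against selective entry only if the people who enrol cannot tell what comes next. Here they know the block length, that each block is balanced, and, from the number itself, where in the block the next patient falls. Any knowledge of an earlier allocation in the same block then bears on the next one.

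Entry leaves room for judgement. It depends on the expected duration of ventilation (Sections 4.2 and 4.3) and on a general exclusion for situations that raise risk or could confound the results (Section 4.3). The monitor also has a say, because Section 4.3 requires the monitor's approval of any eligibility waiver. Recruitment stops at 10 confirmed cases, so the primary comparison rests on very few events.

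Section 5.5 adds a second possible route. Under Appendix C only azithromycin patients use vials; placebo is a plain saline pouch. A count of remaining vials, read beside treatment durations in the case report forms, can therefore hint at arms, and more so when taken part-way through a block.

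**Working it through.** **Inputs.** Block length 4, equal groups, one list per centre, sequential numbers (Section 5.3); sites "for a maximum of 25 study sites although 20 sites are targeted initially" (Section 5.3); sample size "Recruit a total of 120 to 240 patients in order to achieve 100 to 200 assessable cases" (Synopsis).

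**1. Block positions are visible.** 124 − 101 + 1 = 24 numbers per site = 6 × 4. Blocks end at 104, 108, 112, 116, 120 and 124. Average recruitment per site lies between 120/25 = 4.8 and 240/20 = 12 patients, about one to three blocks.

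**2. One patient known.** A block of 4 has 6 equally likely orders. With one allocation known, two of the other three places hold the opposite arm.
- Known patient in position 1, 2 or 3: the next allocation in the block is the opposite arm with probability 2/3.
- Known patient in position 4: the next patient opens a new block, so the probability stays at 1/2.
- Average over the four positions: (3 × 2/3 + 1/2)/4 = 0.625.

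**3. Two or three known among the first three.**
- Two known are on the same arm with probability 1/3, and the rest of the block is then certain. Otherwise (probability 2/3) the remaining places are back to 1/2.
- Three known: the fourth is certain.

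**4. Extreme case: every earlier allocation in the block known.**
- Chance of a correct guess by position: 1/2, 2/3, 1/3 × 1 + 2/3 × 1/2 = 2/3, and 1. Mean = (1/2 + 2/3 + 2/3 + 1)/4 = 17/24 = 70.8%.
- Certain allocations: (1/3 + 1)/4 = 1/3, that is 8 of the 24 positions in the 6 orders.

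**5. With varying, undisclosed lengths.** For block length b, a known patient who is not last gives the opposite arm next with probability (b/2)/(b − 1): 2/3 for b = 4 and 3/5 for b = 6.
- One patient known at a random position, lengths 4 and 6 equally likely: (3 × 2/3 + 1/2 + 5 × 3/5 + 1/2)/10 = 0.60, against 0.625. Simulation with lengths 4, 6 and 8 gives about 0.59.
- All earlier allocations known, simulated 24-patient lists: correct guesses about 69% (lengths 4 and 6) or 67% (4, 6 and 8), against 70.8%.
- Certain allocations in the same setting, lengths 4 and 6, with an observer who knows the possible lengths but not their order: about 6%, against 33%.

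**6. Why single patients count.** Section 11.3 uses a two-sided Fisher test at 0.10. For equal arms of n and 10 cases split 10 − k to k, p = 2 × Σ(j = 0 to k) C(n, j) C(n, 10 − j)/C(2n, 10). Assuming n = 75 per arm (150 in all, inside the planned 100 to 200), 8 v 2 gives p = 0.098 and 7 v 3 gives p = 0.33. One case in the other arm reverses the conclusion.

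**The case against.** The trial is double blind, and the protocol limits unmasking. Section 10.2 restricts envelope opening to medical need, requires the date and reasons in three places, stops study medication and brings in the sponsor, before the break where possible. Envelopes are individual, so each reveals one patient. Section 5.4 forbids the pharmacist to discuss the code, and Section 5.5 postpones supply reconciliation until after unblinding. Several code breaks within one block at one site would be unusual. Even with full knowledge, varying the lengths lowers average guessing accuracy by only a few points.

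All of this stands, and it limits the size of the point. It does not remove it: pharmacist silence does not cover the envelopes or the printed length, and the stock inquiry takes place during the study.

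A reader might infer that any unmasked patient makes the following allocations at that site fully predictable. The arithmetic does not support that. A fourth-in-block patient reveals nothing about later ones, a single known patient never gives more than 2/3, and patients already enrolled when the code is broken cannot be selected. Nor does step 6 show that a biased result is likely. It shows only that a 10-case comparison can turn on one patient.

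**Conclusion.** The point holds as a limited weakness in allocation concealment. A fixed, disclosed block of 4 with sequential numbers per centre raises the chance of guessing the next allocation to 2/3 after one unmasking in positions 1 to 3. It gives certainty only after two same-arm or three unmaskings in one block. The share of one third certain belongs to the extreme case in which every earlier allocation in the block is known, and should not be read as the expected state.

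The actual effect depends on how often patients are unmasked while their block is still open and on whether anyone acts on it. The documents give no figure for either, and with no unmasking the effect is nil. The vial count route is an inference from Section 5.5 and Appendix C; the protocol does not say what the monitor would learn. The case for change is the low cost of the remedy rather than a large demonstrated bias.

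**What to change.** - Generate the centre lists with randomly varying block lengths, for example 4 and 6. Three blocks of 4 and two of 6 in random order still fill 24 numbers (12 + 12).
- Keep the lengths only in a restricted randomization document at the Biometrics Department.
- In Section 5.3 delete the block length and the list of recruitment targets in multiples of four. In Section 5.5 delete the reference to four-patient blocks.
- Have vial stock and resupply handled between the pharmacist and an unblinded supply function, not through the site monitor. Merely switching the monitor's inquiry to calendar dates would not help: vial use would still differ by arm, and inquiries could fall mid-block, when they reveal more.

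Cost: lists regenerated before first supply, short edits to two sections and a separate supply contact. The maximum within-centre imbalance rises from 2 to 3 patients. The benefit is mainly fewer certain allocations (about 33% to 6% under full knowledge with lengths 4 and 6); average guessing accuracy improves little.
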